3.2 Efficacy Endpoints

Primary Efficacy Endpoint(s):

1. Changes from Baseline in non-vellus Target Area Hair Counts (TAHC) using digital image analysis at Week 16.
2. The subject's evaluation of treatment benefit via the Hair Growth Assessment (HGA) questionnaire at Week 16.

Secondary Efficacy Endpoints:

1. Changes from Baseline in non-vellus Target Area Hair Width (TAHW) using digital image analysis at Week 16.
2. Changes from Baseline in non-vellus Target Area Hair Darkness (TAHD) using digital image analysis at Week 16.
3. The subject's evaluation of treatment benefit via the Hair Growth Index (HGI) questionnaire at Week 16.
4. Proportion of subjects with each Investigator's Global Assessment (IGA) grade at Week 16.

3.3 Safety Endpoints

1. Incidence (severity and causality) of any local and systemic adverse events (AEs).
2. Number of subjects with presence (and severity) of the following local skin reactions (LSRs): erythema, edema, erosion, scaling, pruritus, and burning/stinging at each time point.
3. Changes from Baseline in vital signs at each time point.
4. Changes from Baseline in clinical laboratory tests (chemistry [including lipid panel and thyroid function], hematology, and urinalysis, and cardiac biomarkers) at Week 4, Week 8, Week 12, and Week 16.
5. Changes from Baseline in electrocardiogram (ECG) parameters and overall ECG interpretation at Week 4, Week 8, Week 12, and Week 16.

3.4 Pharmacokinetic Endpoints

If plasma concentrations of TDM-105795 are quantifiable, the plasma concentrations will be summarized for active treatment groups.

4. STUDY DESIGN

This is a multi-center, randomized, double-blind, vehicle-controlled, parallel group, multi-dose study of TDM-105795 in male subjects, 18 to 55 years old, with AGA. Approximately 72 subjects with a clinical diagnosis of mild to moderate AGA in temple and vertex region, IIIv to V on the Modified Norwood-Hamilton Scale (i.e., IIIv, IV, and V) who fulfill the inclusion/exclusion (I/E) criteria will be enrolled at approximately 12 study sites in the United States. Subjects will be randomized (1:1:1) to 1 of the 3 investigational products (IPs) listed below. The assigned investigational product (IP) will be applied once daily (1 mL/dose of IP) for 16 weeks, with application to the scalp focusing on the regions that are bald and thinning.

1. TDM-105795 topical solution, 0.0025%
2. TDM-105795 topical solution, 0.02%
3. TDM-105795 topical vehicle solution (Placebo)

Subjects will have 10 study visits (8 in person and 2 via phone): Screening, Baseline/Day 1, and Follow-Up visits at Days 14 (Week 2), 28 (Week 4), 42 (Week 6 via phone), 56 (Week 8), 70 (Week 10 via phone), 84 (Week 12), 112 (Week 16/End of Treatment [EOT]), and 140 (Week 20/End of Study [EOS]). Efficacy will be assessed via IGA, quantitative hair measurements that include TAHC, TAHW, and TAHD, and subject self-assessment (SSA) questionnaires which include HGA and HGI. Safety will be assessed by physical examinations, vital signs, 12-lead ECG, clinical labs (chemistry [including lipid panel and thyroid function], hematology, urinalysis, and cardiac biomarkers), LSRs, and AEs.

4.1 Schedule of Events

Visit	Visit 1	Visit 2	Visit 3	Visit 4	Visit 5	Visit 6	Visit 7	Visit 8	Visit 9 ¹	Visit 10
	Screening	Baseline	Week 2	Week 4	Week 6 Phone	Week 8	Week 10 Phone	Week 12	Week 16 / EOT	Week 20 / EOS
Day	-45 to -3	1	14 ± 3	28 ± 3	42 ± 3	56 ± 3	70 ± 3	84 ± 3	112 ± 3	140 ± 5
Informed Consent	X									
Demographics	X									
Inclusion / Exclusion Assessment	Review	X								
Medical History	X	X								
Concomitant Medications / Concurrent Procedures/Therapies	X	X	X	X		X		X	X	X
Modified Norwood-Hamilton Scale	X									
Drug Screen	X	X								
Alcohol Screen	X	X								
Physical Examination ²	X	X		X		X		X	X	X ³
Height, Weight, and Body Mass Index	X								X	
Vital Signs ⁴	X	X	X	X		X		X	X	X ³
12-Lead ECG ⁵	X	X		X		X		X	X	X ³
Clinical Laboratory Tests ⁶ (chemistry [including lipid panel and thyroid function ⁷], hematology, urinalysis, and cardiac biomarkers ⁸)	X	X		X		X		X	X	X ³
Serology ⁹	X									
Standardized Global Photography ¹⁰	X	X ¹¹		X		X		X	X	
Subject Self-Assessment ¹²				X		X		X	X	
Investigator Global Assessment ¹³				X		X		X	X	
Local Skin Reactions		X ¹⁴	X	X		X		X	X	X
Scalp Micro-Dot Tattoo		X		X ¹⁵		X ¹⁵		X ¹⁵	X ¹⁵	
Standardized Macro Photography ¹⁶		X		X		X		X	X	
PK Blood Draw		X ¹⁷		X ¹⁸		X ¹⁸		X ¹⁸	X ¹⁸	

Visit	Visit 1	Visit 2	Visit 3	Visit 4	Visit 5	Visit 6	Visit 7	Visit 8	Visit 9 ¹	Visit 10
	Screening	Baseline	Week 2	Week 4	Week 6 Phone	Week 8	Week 10 Phone	Week 12	Week 16 / EOT	Week 20 / EOS
Day	-45 to -3	1	14 ± 3	28 ± 3	42 ± 3	56 ± 3	70 ± 3	84 ± 3	112 ± 3	140 ± 5
Randomization ¹⁹		X								
IP Accountability: Dispense (D) / Collect (C)		D	C + D	C + D		C + D		C + D	C	
Subject Diary: Dispense (D) / Collect (C) / Review (R)		D	C+R D	C+R D		C+R D		C+R D	C+R	
Apply IP in Clinic		X								
Adverse Events	X ²⁰	X	X	X	X	X	X	X	X	X

¹ Or early termination visit.

² Assessments will include examination of head and neck, dermatologic (except scalp hair loss), cardiovascular, respiratory, gastrointestinal (abdomen), and gross motor and gait. Clinically significant abnormalities at Visit 1/Screening and Visit 2/Baseline will be recorded as medical history. Any new or worsening clinically significant abnormalities after first dose of IP will be recorded as AEs.

³ To be performed if: 1) there are new or worsening clinically significant abnormalities at the subject's most recent prior evaluation or 2) as warranted based on subject's current medical condition, in the opinion of the investigator. In addition, at the discretion of the investigator, most recent clinical labs or ECGs that are out of the normal range may also be repeated at this visit, if viewed as clinically significant by the investigator.

⁴ Assessments will be made after the subject has rested in a seated position for at least 5 minutes.

⁵ 12-lead ECGs will be performed after the subject has rested for at least 10 minutes in the supine position.

⁶ The subject must have at least one fasting set of labs prior to treatment being administered at Visit 2/Baseline. It is preferred that subjects be fasting (approximately 8 hours) for both Visit 1/Screening and Visit 2/Baseline and, if possible, for all clinical laboratory testing; however, if a subject arrives at the clinic without fasting for at least 8 hours, laboratory specimens may be collected as non-fasting, at the discretion of the investigator, and with the appropriate fasting status documented on the lab requisition form.

⁷ Free T4, Total T3, and TSH.

⁸ CK-MB, Troponin T, and NT-proBNP.

⁹ HIV, Hepatitis B and C screen.

¹⁰ Global photography (for SSA and IGA) must occur prior to macro photography. At Screening, global reshoots must occur in time to ensure the global photos are of an acceptable quality for assessment, as verified by the vendor, prior to Visit 2/Baseline. No reshoots of global photos will occur for subsequent scheduled visits.

¹¹ If Screening photos are not adequate and re-shoot prior to Baseline was not performed, additional global photo(s) will be taken at Baseline.

¹² The subject must refer to their baseline and current visit global photos when completing the SSA.

¹³ The evaluator must refer to the subject's 'baseline' global photos (taken at Screening) and compare them to the current visit's photos of subject's scalp hair growth.

¹⁴ LSRs will be assessed prior to dosing.

¹⁵ Check scalp micro-dot tattoo and re-apply if it has significantly faded at any visit during the study.

¹⁶ Macro photography (for TAHC, TAHW, and TAHD) must occur after global photography. Macro photo reshoots must occur within 7 days after the visit.

¹⁷ Baseline PK blood sample, in the clinic, will be collected pre-application and a second PK blood sample 1-4 hours post-application.

¹⁸ PK blood samples will be collected in the clinic 1 to 4 hours after at home IP application by the subject.

¹⁹ Subject will be randomized using the IWRS.

²⁰ During any wash out and screening periods, any changes in the health of subjects should be recorded as changes in medical history unless an event occurred as a result of a study-related procedure and is unanticipated; in such cases, the event should be recorded as an AE and reported to the Institutional Review Board (IRB) as an “unanticipated problem” in accordance with local procedures.

5. DEFINITIONS

- The **Study Day** is the day of the study relative to the first dose (Baseline Visit / Treatment #1) of the IP. Study day is derived as:
Assessment visit date – First dose date + 1.
- The **Baseline Assessment** is defined as the last non-missing measurement collected at Screening or Baseline (Day 1) visit prior to the first administration of the IP. For subjects without approved Baseline photos an appropriate imputation method may be considered for Baseline values.
- **Post-baseline** is defined as a measurement taken after the administration of the first dose of IP.
- **Change from baseline** will be calculated as:

$$\text{Post-baseline value} - \text{Baseline value}$$

Correspondingly, **percent change from baseline** will be calculated as:

[figure not shown]
$$100 \times (\text{Post-baseline value} - \text{Baseline value}) / \text{Baseline value}$$

6. CLINICAL EVALUATIONS

6.1 Modified Norwood-Hamilton Scale

The Modified Norwood-Hamilton Scale will be used at Visit 1/Screening to classify the pattern of hair loss and determine subject eligibility. Subjects must have mild to moderate AGA in the temple and vertex region, rating IIIv to V on the Modified Norwood-Hamilton Scale (i.e., IIIv, IV, and V), to be eligible for the study. The Modified Norwood-Hamilton Scale describes the most regular patterns for male pattern baldness.

Figure 6.1-1 Modified Norwood-Hamilton Scale Describing Male Pattern Baldness

- **Type I.** No recession or very minimal recession along the anterior border of the hairline in the frontotemporal region.
- **Type II.** The anterior border of the hair in the frontotemporal region has triangular areas of recession which tend to be symmetrical. These areas of denudation extend no further posteriorly than approximately 2 cm anterior to a line drawn in a coronal plane between the external auditory meatus. Hair also is lost, or sparse, along the midfrontal border of the scalp, but the depth of the affected area is much less than in the frontotemporal region.
- **Type III.** This represents the minimal extent of hair loss considered sufficient to represent baldness. Most type III scalps have deep frontotemporal recessions which are usually symmetrical and are either bare or very sparsely covered by hair. These recessions extend further posteriorly than a point which lies approximately 3 cm anterior to a coronal line drawn between the external auditory meatus.
- **Type IV.** The frontal and frontotemporal recession is more severe than in type III. Also, there is sparseness or absence of hair on the vertex area. These areas are extensive but separated from each other by a band of moderately dense hair that extends across the top. This band joins the fully haired fringe on each side of the head.
- **Type V.** The vertex region remains separated from the frontotemporal region. The separation is now not as distinct, because the band of hair across the crown has become narrower and sparser. Both the vertex and frontotemporal areas of hair loss have become larger.
- **Type VI.** The bridge of hair that crossed the crown in the previous type is now gone. The frontotemporal and vertex regions of hair loss have become confluent, and in addition the entire area of hair loss has increased laterally and posteriorly.
- **Type VII.** This is the most severe form of male pattern baldness. All that remains is a narrow horseshoe-shaped band of hair which begins laterally just anterior to the ear and extends posteriorly on the sides and quite low on the occiput. This hair is usually not dense and frequently is fine. The hair is also extremely sparse on the nape of the neck and in a

semicircle over both ears. It should be noted that the anterior border of this band on each side of the head has receded posteriorly to just in front of the ears.

6.2 Investigator's Global Assessment

The evaluator will use standardized global photos (i.e., a vertex view and a superior view) of the subject's scalp taken at Visit 1/Screening and will compare them to the current visit's photos of the subject's scalp hair growth using the Canfield Review application. The evaluator will assess the subject's scalp hair growth using the following 7-point scale: greatly decreased (-3), moderately decreased (-2), slightly decreased (-1), no change (0), slightly increased (1), moderately increased (2), and greatly increased (3).

6.3 Subject Self-Assessment

The subject will use the standardized global photos (i.e., a vertex view and a superior view) of the subject's scalp taken at Visit 1/Screening and will compare them to the current visit's photos of subject's scalp hair growth for HGA and HGI which comprise the SSA.

6.3.1 Hair Growth Assessment

Scalp hair growth will be compared from baseline using the following 7-point scale: greatly decreased (-3), moderately decreased (-2), slightly decreased (-1), no change (0), slightly increased (1), moderately increased (2), and greatly increased (3).

6.3.2 Hair Growth Index

Scalp hair growth will be compared from baseline using the following 7-point scale: much less (-3), moderately less (-2), slightly less (-1), the same amount (0), slightly more (1), moderately more (2), and much more (3) for the following 3 questions:

1. "Since the start of treatment, when I look at my thinning area, I can see ... (scalp)";
2. "Since the start of treatment, my hair now covers ... (scalp)"; and
3. "Since the start of treatment, the appearance (thickness/quality/ amount) of the thinning area on my head is ..."

7. SAFETY EVALUATIONS

7.1 Physical Examination

Physical examinations will be performed per the Schedule of Events (SOE). Assessments will include examination of head and neck, dermatologic (except the indication being studied), cardiovascular, respiratory, gastrointestinal (abdomen), and gross motor and gait. Clinically significant abnormalities at Visit 1/Screening and Visit 2/Baseline will be recorded as medical history. Any new or worsening clinically significant abnormalities after first dose of IP will be recorded as AEs.

7.2 Vital Signs

Vital signs including temperature, systolic and diastolic blood pressure, heart rate, and respiration rate will be measured per the SOE. Assessments will be made after the subject has rested in a seated position for at least 5 minutes. Height, weight, and Body Mass Index (BMI) will also be measured at Visit 1/Screening and Visit 9/EOT.

7.3 Electrocardiogram

ECGs will be performed per the SOE. 12-lead ECGs will be performed after the subject has rested for at least 10 minutes in the supine position. ECG results will be recorded on the appropriate eCRF.

7.4 Local Skin Reactions

LSRs will be collected per the SOE. LSRs of erythema, edema, erosion, scaling, pruritus, and burning/stinging will be assessed using a 5-point ordinal scale (0=none, 1=minimal, 2=mild, 3=moderate, and 4=severe). Only reactions that require medical intervention (e.g., prescription medication) will be documented as AEs. Any reactions to the IP that are not listed above will be recorded as AEs.

7.5 Pharmacokinetic Tests

Blood samples will be collected per the SOE. At Visit 2, subjects will be dosed in the clinic and a PK blood sample will be collected before the first dose as well as 1-4 hours post-dose. At Visits 4, 6, 8, and 9, PK blood samples will be collected. These visits should be scheduled so that PK sample collection will occur 1 to 4 hours after the subject has self-applied the IP application at home. Sampling date/times will be recorded on the appropriate eCRFs. Concentrations of TDM-105795 in plasma will be determined from these samples using validated analytical methods.

7.6 Laboratory Tests

Blood and urine specimens will be collected per the SOE for chemistry (including lipid panel and thyroid function), hematology, urinalysis, and cardiac biomarkers. It is preferred that subjects be fasting (approximately 8 hours) for all laboratory assessments; however, if a subject arrives at the clinic without fasting for at least 8 hours, laboratory specimens may be collected as non-fasting, at the discretion of the investigator, and with the appropriate fasting status documented on the lab requisition form. However, the subject must have at least one fasting set of labs prior to treatment being administered on Visit 2/Baseline. Any new or worsening abnormal test results that are identified as clinically significant after Baseline will be recorded as AEs.

The following clinical safety laboratory tests will be performed:

LABORATORY TESTS		
Chemistries	Hematology	Urinalysis
Albumin	Hemoglobin	Color
Alkaline phosphatase	Hematocrit	Appearance/Clarity
ALT (SGPT)	MCV	Bilirubin
AST (SGOT)	MCH	Blood
Bilirubin, total	MCHC	Glucose
Calcium	RBC (Erythrocytes)	Ketones
Carbon Dioxide §	WBC (Leucocytes)	Leukocyte Esterase
Chloride	RDW	Nitrite
Creatinine	Differential count	pH
GGT	Basophils	Protein
Glucose (fasting, preferred)	Eosinophils	Specific gravity
LDH	Lymphocytes	Urobilinogen
Phosphate	Monocytes	Microscopic analysis (if indicated)
Potassium	Neutrophils	
Protein, total	Platelets	
Sodium		
Urea (BUN)	Cardiac Biomarkers	
Uric acid	CK-MB	
Lipid Panel	Troponin T	
Cholesterol, total	NT-proBNP	
Triglycerides		
Thyroid Function		
TSH		
Total T3		
Free T4		

8. STATISTICAL METHODS

8.1 Estimands for Efficacy Endpoints

Treatment conditions of interest	
Condition under study: AGA in males.
 
Investigational Drugs:
 
• TDM-105795 topical solution, 0.0025%• TDM-105795 topical solution, 0.02% 
Comparator Drug:
 
• TDM-105795 topical vehicle solution (Placebo)
Population	Male subjects 18-55 years of age with mild to moderate AGA
Endpoints	
Primary Efficacy Endpoint(s):
 
1. Changes from Baseline in non-vellus TAHC using digital image analysis at Week 16.2. The subject's evaluation of treatment benefit via the HGA questionnaire at Week 16. 
Secondary Efficacy Endpoint(s):
 
1. Changes from Baseline in non-vellus TAHW using digital image analysis at Week 16.2. Changes from Baseline in non-vellus TAHD using digital image analysis at Week 16.3. The subject's evaluation of treatment benefit via the HGI questionnaire at Week 16.4. Proportion of subjects with each IGA grade at Week 16.
Population level summary	
Primary endpoints: The changes from Baseline at Week 16 in the non-vellus TAHC will be evaluated by analysis of covariance (ANCOVA) where the model includes treatment and site as factors and the baseline TAHC as the covariate. Least squares means (LSM) will be presented for pairwise comparisons of treatment groups. Descriptive statistics will be also provided by treatment group for each time point for non-vellus quantitative hair measurements.
 
The HGA will be evaluated at Week 16 descriptively (frequencies and percentages) for each assessment category by treatment group.
 
Secondary endpoints: The changes from Baseline at Week 16 with respect to non-vellus TAHW and TAHD will be evaluated by ANCOVA with treatment group and site as fixed factors, and the corresponding baseline value as the covariate. LSM will be presented for pairwise comparisons of treatment groups.

	
Each of the 3 subject-rated questions that comprise the HGI will be summarized by frequency and individual response category at Week 16 by treatment group.
 
The IGA will be summarized by frequency and individual response category at Week 16 by treatment group.

ICEs and strategies to handle ICEs	A treatment policy strategy will be employed where no ICEs will be defined. No imputation for missing data will be performed.

8.2 General Considerations

All statistical processing will be performed using SAS®. Summary tables (descriptive statistics and/or frequency tables) will be provided for screening and/or baseline variables, efficacy variables, and safety variables. Continuous variables will be summarized by descriptive statistics including the number of subjects with non-missing data (n), mean, median, standard deviation, minimum, and maximum values by treatment group. Means will be presented to one additional decimal place and the associated standard deviation will be presented to 2 additional decimal places than the presentation level of the respective subject data. Minimum and maximum values will be presented using the same number of decimal places as the subject data. Frequency counts and percentage of subjects within each category will be provided for categorical data. Summaries will be provided for each treatment group. No formal tests of hypotheses will be performed. If present, p-values, will be provided for descriptive purposes only and will be reported to 3 decimal places.

In general, all summary tables will be supported by relevant subject data listings which will be sorted by treatment, study site, subject identification, and visit, as applicable. Figures may be created to aid in the interpretation of results.

8.3 Analysis Populations

8.3.1 *Safety Population*

The Safety population will include all randomized subjects who received and applied the IP.

8.3.2 *Intent-to-Treat Population*

The intent-to-treat (ITT) population will include all randomized subjects who were dispensed the IP.

8.3.3 *Per-Protocol Population*

The per-protocol (PP) population will include a subset of the ITT population who completed the Visit 9 (Week 16/EOT) efficacy assessments without significant protocol deviations.

8.3.4 *PK Population*

The PK population will include those subjects in the ITT population with at least 1 measurable concentration value.

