--	--

	
IP dispensed and weight of IP returned), and the mean daily amount of IP applied (total amount of IP applied divided by the duration of treatment) will be calculated.
 
Physical Examinations
 
Findings from physical examinations will be recorded in medical history (from assessment at Screening and Baseline) or as AEs (from assessments after first dose).
 
Vital Signs
 
Descriptive statistics of vital signs (temperature, systolic and diastolic blood pressure, heart rate, and respiration rate), including height, weight, and BMI will be provided by treatment group.
 
Electrocardiograms
 
ECGs will be evaluated for any material changes during the study period. Descriptive statistics of ECG parameters will be provided by treatment group. Changes in overall interpretation of the ECG from Baseline to Weeks 4, 8, 12, and 16 will be examined using shift tables.
 
Clinical Laboratory Tests
 
Clinical laboratory tests will be evaluated for any material changes during the study period. All laboratory data (chemistry [including lipid panel and thyroid function], hematology, urinalysis, and cardiac biomarkers [CK-MB, Troponin T, and NT-proBNP]) will be listed and reported in the units received from the laboratory. Shift tables by analyte and by out of range flag will be presented to facilitate the evaluation of change from Baseline to Weeks 4, 8, 12, and 16.
 
Local Skin Reactions
 
LSRs (erythema, edema, erosion, scaling, pruritus, and burning/stinging) will be summarized by frequency and severity of each individual LSR for each treatment group.
 
Adverse Events
 
All AEs reported during the study will be listed, documenting course, severity, investigator assessment of the relationship to the IPs, and outcome. Verbatim terms on the eCRFs will be linked to preferred terms (PTs) and system organ class (SOC) using the Medical Dictionary for Regulatory Activities (MedDRA) mapping system. The PTs and SOC will then be tabulated. All reported AEs will be summarized by the number of subjects reporting AEs, SOC, PT, severity, and relationship to IP by treatment group.
 
Pharmacokinetics Analyses:
 
A PK analysis will be conducted on the PK population. PK results will be summarized using descriptive statistics for each active treatment group.

--	--

SCHEDULE OF EVENTS

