17.4.3 Pharmacokinetic Analyses

A PK analysis will be conducted on the PK population.

PK results will be summarized using descriptive statistics for each active treatment group.

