8.6 Subject Disposition

The number and percent of subjects who were enrolled in the study, in each analysis population, who completed the study, who withdrew from the study, and their reasons for withdrawal will be summarized by treatment groups.

The number of subjects enrolled by site and by visit will be summarized for all analysis populations (safety, ITT, PP and PK).

Informed consent information and subject eligibility status will be provided in a subject listing.

Subjects who were screen failures, along with their reason for screen failure will be listed.

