8.7 Screening and Baseline Assessments

8.7.1 *Demographics*

Demographic characteristics including sex, age, race, and ethnicity will be summarized descriptively by treatment group for the safety, ITT, PP, PK populations. Demographic data for screen failures will be summarized separately.

8.7.2 *Physical Examination*

Physical examination abnormalities will not be provided separately, but will be included with medical history listing.

8.7.3 *Baseline Modified Norwood-Hamilton Scale*

Modified Norwood-Hamilton Scale grade recorded at screening will be tabulated by treatment group for the safety, ITT, and PP populations.

8.7.4 *Baseline Standardized Macro Photography Measurements*

Baseline quantitative hair measurements will include TAHC, TAHW, and TAHD, which will be calculated using digital image analysis from standardized macro photos. TAHC, TAHW, and TAHD for non-vellus and vellus/vellus-like (miniaturized) hair will be descriptively summarized by treatment group for the safety, ITT, and PP populations.

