8.8.1.3 Dosing Compliance

Descriptive statistics will be used to summarize the total number of applications for the ITT, PP and PK populations. Subjects who apply at least 80% of the expected total number of applications and have no other evidence of material dosing non-compliance will be considered to be compliant with IP dosing.

8.8.2 *Statistical / Analytical Issues*

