8.10 Pharmacokinetic Analyses

A PK analysis will be conducted on the PK population. If plasma concentrations of TDM-105795 are quantifiable, the plasma concentrations will be summarized for active treatment groups.

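### The PK population is selected on having a measurable concentration, and no below-limit rule is stated, so the planned concentration summary can overstate systemic exposure (minor)

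*SAP*

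**What the plan says.** SAP 8.3.4 defines the set: "The PK population will include those subjects in the ITT population with at least 1 measurable concentration value". The Protocol synopsis (Study Populations) and Protocol 17.4 use the same sentence.

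Protocol 17.4.3 then says "A PK analysis will be conducted on the PK population" and "PK results will be summarized using descriptive statistics for each active treatment group". SAP 8.10 keeps the first of these sentences and adds: "If plasma concentrations of TDM-105795 are quantifiable, the plasma concentrations will be summarized for active treatment groups". Under SAP 8.2, continuous variables are reported as n, "mean, median, standard deviation, minimum, and maximum values by treatment group".

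Three further points matter.

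- *Measurable* is not defined. Protocol 1 (Background) uses the word for levels not below 5 pg/mL, the limit of quantification in Studies 101 and 102. No assay limit is stated for the present trial.
- No rule is given for samples below the limit. SAP 8.8.2.2 covers efficacy endpoints and incomplete dates, and SAP 8.11 is marked not applicable.
- The set is used elsewhere. SAP 8.6 reports by treatment group "The number and percent of subjects who were enrolled in the study, in each analysis population, who completed the study". In SAP 8.7.1 demographics "will be summarized descriptively by treatment group for the safety, ITT, PP, PK populations". SAP 8.8.1.3 says "Descriptive statistics will be used to summarize the total number of applications for the ITT, PP and PK populations".

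**The concern.** Membership of the set depends on the result that the set is used to summarize. A subject who is dosed and sampled at every visit, with all results below the limit, carries information about exposure, namely that it is low. The rule removes that subject from the denominator, and the mean for the dose group is then conditional on detection.

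PK is part of the third study objective. Protocol 2 (Rationale) rests the case for the product partly on little or no systemic absorption. A reader will take a table of concentrations by dose as exposure in treated subjects. If nothing at all is quantifiable, SAP 8.10 promises no summary, although none detected out of the number sampled, by dose and visit, would be the result most relevant to that rationale.

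**Working it through.** **Inputs.** There are 24 subjects per arm (24 × 3 = 72, as in the synopsis). Each subject has five post-dose samples: Visit 2 after dosing, then Visits 4, 6, 8 and 9. The limit of 5 pg/mL is assumed from Studies 101 and 102. The documents give no PK figure to reproduce, no concentration distribution and no detection rate. The share admitted, *p*, is therefore varied.

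**Step 1: identity, free of any distribution.** Let *M* be the PK-set mean and *s* the value substituted for a below-limit sample. With equal numbers of samples per subject, each excluded subject has mean *s*, so

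mean over all sampled = *pM* + (1 − *p*)*s*, and

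PK-set mean − mean over all sampled = (1 − *p*)(*M* − *s*).

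For *s* no higher than the limit this is never negative, and it is zero at *p* = 1. For *s* = 0 the ratio is exactly 1/*p*, so at *p* = 0.25 it is 1/0.25 = 4.0.

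**Step 2: other substituted values.** These need an assumed distribution. The simulation used 100,000 subjects with lognormal concentrations and between-/within-subject log-SDs of 0.8/0.5, 0.5/0.5 and 1.0/0.7. The median was set to give each *p*. Entries are the PK-set mean divided by the mean over all sampled; ranges run over the three SD pairs.

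| *p* | subjects of 24 | *s* = 0 (exact) | *s* = half the limit | *s* = the limit |
|---|---|---|---|---|
| 0.10 | 2.4 | 10.0 | 1.41–1.75 | 1.09–1.25 |
| 0.25 | 6 | 4.0 | 1.40–1.73 | 1.10–1.30 |
| 0.50 | 12 | 2.0 | 1.31–1.52 | 1.11–1.29 |
| 0.75 | 18 | 1.33 | 1.17–1.25 | 1.08–1.18 |
| 0.90 | 21.6 | 1.11 | 1.07–1.10 | 1.04–1.08 |
| 0.95 | 22.8 | 1.05 | 1.04–1.05 | 1.03–1.04 |

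Check of one cell against Step 1 (log-SDs 0.8/0.5, *p* = 0.25, half the limit): the means are 5.16 and 3.16 pg/mL, a difference of 2.00 and a ratio of 5.16/3.16 = 1.63. The identity gives 0.75 × (5.16 − 2.5) = 1.995.

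**Step 3: below-limit samples omitted.** Excluded subjects then contribute no values under either definition, so the set does not change the mean. Every value averaged is at least the limit, and so is every mean. At *p* = 0.25 the mean of quantifiable samples was 3.0 to 4.7 times the true mean over the three SD pairs.

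**Step 4: how many would be excluded.** Study 101 had no detections in 8 + 8 + 8 = 24 active subjects, after single doses of at most 0.1 mg. Study 102 gave both present strengths daily for 4 weeks and reports only that levels were not consistently measurable. This trial gives 0.025 or 0.2 mg daily. Substantial exclusion is plausible on this evidence, but no rate follows from it, and near-complete detection is not ruled out.

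**The case against.** **The effect on the mean depends on a below-limit rule that the plan does not contain.** This stands. SAP 8.2 counts subjects with non-missing data and SAP 8.10 speaks of quantifiable concentrations, so omitting below-limit samples is an open reading. Under it the population rule adds no bias to the mean, and the gap is the missing rule. A reader might infer that the means by dose are too high whenever detection is incomplete, because of the set. The documents support that only if a value is substituted. Even then, too high means relative to all sampled subjects under the same rule, not relative to the true mean. With zero substituted, *p* = 0.50 and log-SDs 0.5/0.5, the PK-set mean is 3.28 against a true mean of 3.61 pg/mL.

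**Half the limit can be the larger error.** This also stands. With assumed between-/within-subject CVs of 80%/60% and true medians of 0.25 to 1 pg/mL, substituting half the limit puts the mean over all sampled subjects at 6.7 to 1.8 times the true mean. At a median of 1, that is 2.68/1.49 = 1.80, against 4.13/2.68 = 1.54 from the set. Redefining the set while keeping a substituted mean would not give a sound summary where detection is rare.

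**Disclosure.** SAP 8.6 shows the share in the set by arm, and SAP 8.2 supports the tables with listings, so a careful reader could see the exclusion. That is a real mitigation. It does not correct the summary, and it does not give detection counts by visit.

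**Definition.** Equating *measurable* with at or above the limit is inferred from the background text. If a valid assay result is meant, the sentence still needs to say so.

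**Direction.** The error overstates exposure, against the sponsor's own low-absorption rationale, so it does not flatter the product.

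**Conclusion.** The concern holds in a limited form, and it is minor. The PK set is chosen on its own outcome and the PK summary uses that set alone. Under any substitution rule no higher than the limit, the mean is inflated by (1 − *p*)(*M* − *s*), which becomes negligible as detection nears completeness. With a quarter of subjects admitted, the factor is 4.0 for zero and about 1.4 to 1.7 for half the limit. The first figure is exact given equal samples per subject; the second rests on assumed lognormal distributions and a 5 pg/mL limit. The actual size cannot be computed from the documents.

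A reader might also infer that the comparison between the two doses, which are 8-fold apart, is distorted by a known amount or in a known direction. The documents do not support that. Under a dose-proportional lognormal model (CVs 80%/60%, five samples per subject), low/high medians of 0.5/4 pg/mL imply medians of 0.5, 1 and 2 in the Study 101 arms, with 1.9%, 11.2% and 36.4% of subjects detected. The chance of no detections in 24 is then 0.981⁸ × 0.888⁸ × 0.636⁸ = 0.009. Higher medians fit worse. At 0.25/2, where that chance is 0.32, the inflation is similar in the two arms (1.38 and 1.48), with the larger one at the high dose. Single dosing in Study 101 limits this check.

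No test, decision rule, efficacy analysis or safety analysis rests on the PK summary.

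**What to change.** 1. Define the PK population as subjects who applied at least one dose of IP and have at least one post-dose plasma sample with a valid assay result, including results below the limit.
2. For each active dose and visit, report the number quantifiable over the number sampled as the main PK result, whether or not any value is quantifiable.
3. State the assay limit and one below-limit rule before unblinding.
4. Where most samples in a cell are below the limit, report the median as below the limit, with the maximum and the detected count, rather than a mean driven by substituted values.

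Item 1 needs items 2 to 4. Changing the population alone does nothing if below-limit samples are omitted, and leaves a mean dominated by the substituted value if they are not.

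Cost: either an SAP change to 8.3.4 and 8.10, with the departure recorded in SAP section 9 (which now lists no changes), or a protocol amendment with IRB approval under Protocol 18.4. The PK-population entries in the disposition, demographics and dosing-compliance tables (SAP 8.6, 8.7.1 and 8.8.1.3) change with the definition. No new samples are needed.
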